5. AMENDMENTS AND UPDATES

None. Updated version 2.0 dated 06 December 2017 according to the D195 Joint Rapporteurs Assessment Report. Afterwards updated version 3.0 dated 13 December 2017 according to additional Rapporteurs indication. Additional afterwards version 4.0 dated 02 March 2018 and version 5.0 dated 09 July 2018 have been issues according to PRAC evaluation according to EMA request. A further version 6.0 has been issued after PRAC subsequent evaluation. The version 7.0 has been issued after EMA request. The version 8.0 has been issued after EMA further request to be added to par. 9.2.6.

6. MILESTONES

Milestone	Planned date	Planned date calendar time
Registration in the EU PAS	Registration in the EU PAS	31/03/2019
register	register will be performed before	
	the first patient is included	
Start of data collection	7-8 months from CHMP/PRAC	30/09/2019
	Protocol Approval	
Interim report	Yearly, as part of annual re-	By March 23 rd of each year
	assessment	
End of data collection	Not applicable, as an indefinite	Not applicable
	enrolment period is foreseen	
Final report of study results	Within 6 months from End of	Not applicable
	data collection when it will be	
	defined	

EU PAS register=European Union electronic register of post-authorisation studies

7. RATIONALE AND BACKGROUND

7.1 Background

Alpha-mannosidosis is rare lysosomal storage disorder caused by deficiency of alpha-mannosidase, a lysosomal enzyme involved in the catabolism of glycoproteins [1]. The main effect of this deficiency is the accumulation of mannose-rich oligosaccharides in the tissues. Alpha-mannosidosis is caused by mutations in the MAN2B1 (mannosidase alpha class 2B member 1) protein-coding gene, leading to the production of a dysfunctional or non-functional alpha-mannosidase. Deficiency in alpha-mannosidase is inherited in an autosomal recessive manner. The clinical variability of alpha-mannosidosis is considerable, encompassing a continuum ranging from mild to severe. There is a broad phenotypic variation of manifestations, including intellectual disabilities, hearing impairment, motor function disturbances, facial coarsening, musculoskeletal abnormalities, immune deficiency, corneal opacities, psychiatric symptoms, aseptic destructive arthritis and metabolic myopathy. At birth, alpha-mannosidosis patients appear normal, but their condition progresses over several decades, rendering most patients wheelchair-dependent over the course of adulthood. Neurological findings, mental retardation, skeletal deformations and hearing impairment are foremost leading to the initiation of a diagnostic process in patients with alpha-mannosidosis. Biochemical testing of alpha-mannosidase activity in leukocytes forms the basis of diagnosis, and detection of vacuoles in lymphocytes is seen in the peripheral blood of 90% of the patients [2]. Excretion of mannose-rich oligosaccharides in urine can also be demonstrated. Molecular genetic testing of

Clinical Protocol Number: CLI-LMZYMAA1-12

Clinical Protocol Version Number: 8.0

Date: 01 February 2019

MAN2B1 and identification of two disease-causing mutations can contribute to establishing the diagnosis.

Lamzede (velmanase alfa, henceforth referred to as Lamzede) is a recombinant human lysosomal alpha-mannosidase product, developed as an intravenous enzyme replacement therapy (ERT) for the treatment of alpha-mannosidosis. The safety and efficacy of Lamzede in adults and children (\geq 6 years old) has been evaluated in 33 patients (20 males and 13 females; 19 children [paediatric group, aged younger than 18 years] and 14 adults; median age 17.1 years, range 6.0-35 years) in five clinical studies (three exploratory Phase I to IIb studies, one Phase III pivotal study and one Phase III long-term efficacy and safety evaluation (rhLAMAN-10) in all patients previously enrolled in clinical trials with under-treatment data for up to 48 months).

The rhLAMAN-10 open-label, uncontrolled, phase III study encompassed an integrated database created by pooling cumulative databases from all studies with Lamzede together with an additional long-term assessment endpoint. Statistically significant improvements were detected in serum oligosaccharide levels, 3-minute stair climb test (3MSCT) and pulmonary function over time, up to the last observation. The effects of Lamzede were more evident in patients younger than 18 years. Descriptive evidence of improvement was also documented in several additional clinical endpoints, including serum immunoglobulin G (IgG), Bruininks-Oseretsky Test Of Motor Proficiency–2nd Edition (BOT-2) subdomains and Childhood Health Assessment Questionnaire (CHAQ) Disability Index, CHAQ visual analogue scale (VAS) Pain, European Quality of Life Five Dimension Five Level Scale (EQ-5D-5L) Health Index. A progressive improvement from baseline was also evident in the 6-minute walk test (6MWT). For further details, refer to the Lamzede Summary of Product Characteristics (SmPC).

A multi-domain post-hoc responder analyses was conducted across the pharmacodynamics (serum oligosaccharide response only), functional (3MSCT, 6MWT and Forced Vital Capacity (FVC) % predicted) and quality of life (CHAQ disability index and CHAQ VAS pain) domains.

A clinically significant response for each domain was claimed when at least one parameter of the domain improved beyond the proposed MCID.

In the overall responder analysis, a patient was qualified as responder to treatment if response criteria was reached in at least two domains. The alpha-mannosidosis Response Model generated as part of this approach is depicted in Figure 1.

Figure 1 Alpha-Mannosidosis Treatment Response Models Treatment Response Model

Chiesi	
Clinical Protocol Number: CLI-LMZYMAA1-12	
Clinical Protocol Version Number: 8.0	Date: 01 February 2019

Source: Provided by Chiesi

Based on the MCID-based Treatment Response Model, the Global Response to Treatment (GRT) of rhLAMAN-05 shows a discernible treatment difference between the two groups, with a clinical response in at least two domains at 12 months observed in 87% of patients treated with velmanase alfa compared to 30% in placebo. Moreover, 13% treated patients but none of the placebo patients reported a clinically-significant response in all three domains (Figure 3).

In the single-arm, integrated analysis from rhLAMAN-10 study, a remarkably similar proportion of 79% of patients showed a significant response in at least two domains at 12 months, 24% in all three. The proportion increases at Last Observation with a clinically meaningful response in at least two domains achieved in 88% patients (100% of paediatric patients and 71% of adult patients) and in at least three domains in 45% patients (53% of paediatric patients and 36% of adult patients) (Figure 2). The proposed domains are aligned with the representation of (a) the clinical burden, (b) the endpoints hierarchy defined with the CHMP, (c) the measurements of the benefit perceived by the patients (health-related QoL).

Figure 2 Global Response to Treatment in rhLAMAN-10 Study Integrated Analysis

Collesi	
Clinical Protocol Number: CLI-LMZYMAA1-12	
Clinical Protocol Version Number: 8.0	Date: 01 February 2019

The most common adverse reactions observed during treatment with Lamzede were weight increase (18%), infusion-related reactions (9%), diarrhoea (12%), headache (9%), arthralgia (9%), increased appetite (6%) and pain in the extremities (6%). A total of two serious adverse reactions (loss of consciousness in one patient and acute renal failure in one patient) considered possibly related to study treatment were observed; both cases recovered without sequelae. For further safety information, refer to the Lamzede SmPC.

Lamzede is indicated in patients with alpha-mannosidosis. The marketing authorisation in the EU was granted for Lamzede with European Commission implementing decision of 23rd March 2018. Lamzede is the only authorised treatment for alpha-mannosidosis in the European Union (EU). Prior to its approval, treatment focused on the relief of symptoms, and prevention of complications and impairments, with treatments and procedures designed individually based on symptoms and age. Bone marrow transplantation has been used as a therapeutic strategy for alpha-mannosidosis, but comes with a risk of mortality and morbidity. Palliative treatments include physiotherapy, respiratory physiotherapy or antibiotic treatment for recurrent infections. Prevention of the disease is restricted to prenatal diagnosis and carrier identification.

7.2 Rationale

The Registry is being conducted as an EU Risk Management Plan (EU-RMP) Additional Pharmacovigilance Activities. Lamzede received Orphan Drug Designation in both the EU and the United States, and the marketing authorisation approval in the EU is sought under exceptional circumstances. In connection to Lamzede marketing authorization and its Risk Management Plan, the Alpha-mannosidosis registry is requested to obtain long term data on effectiveness and safety of treatment with Lamzede; furthermore, the Registry will expand the current understanding of alpha-mannosidosis by collecting natural history data, disease modifiers and confounder factors in alpha-mannosidosis patients despite the therapeutic treatment they are receiving.

This study will be conducted in compliance with the Declaration of Helsinki (1964 and amendments), current International Council for Harmonisation (ICH) E6 Good Clinical Practice (GCP) as far as applicable, in accordance with the obligation in the framework of a marketing authorisation granted

Clinical Protocol Number: CLI-LMZYMAA1-12	
Clinical Protocol Version Number: 8.0	Date: 01 February 2019

under exceptional circumstances (category 2 of studies in Good pharmacovigilance practices [GVP] Module V) and all other applicable laws and regulations.

8. RESEARCH QUESTION AND OBJECTIVES

Primary Objective

- To assess the long-term effectiveness and safety of treatment with Lamzede under conditions of routine clinical care.
- In terms of effectiveness, the primary focus of the registry is to estimate the Global Treatment Response rate as percentage of patients qualified as responders by aggregately assessing oligosaccharides in serum (umol/L), (GTR-Pharmacodynamic Domain), 3MSCT (step/min), 6MWT (mt), FVC (% of predicted) (GTR-Functional Domain) and QoL based on CHAQ VAS-Pain and CHAQ- Disability Index (GTR-QoL Domain).
- In terms of safety, the rate of AEs (including ADA, IRRs and Hypersensitivity as identified risks) in the treated patients will be the main research of the study.

Secondary Objectives

- To characterize the alpha-mannosidosis population, including clinical manifestation, progression and natural history.
- In particular, oligosaccharides in serum (umol/L), endurance based on 3MSCT (step/min), 6MWT (m) and 2MWT (m) assessment, respiratory function through FVC (as litre and as percentage of predicted), hearing function with PTA, length and rate of infections (requiring or not antibiotics), rate of psychotic events, immunological status as per serum IgG, IgA and IgM, and QoL assessed by EQ-5D-5L, Zarit Burden Interview, CHAQ, Behavior Checklists (prescholar, scholar, adult and older adult) will be adopted for characterizing the alpha-mannosidosis population
- Rate of incidence of acute renal failure and loss of consciousness (as potential risks under Lamzede treatment), change in vital signs (SBP, DBP), laboratory tests (haematology and chemistry), physical examination and ECG will also be monitored.

9. RESEARCH METHODS

9.1 Study Design

The Registry is a multi-centre, multi-country, non-interventional, prospective cohort including alpha-mannosidosis patients, despite any treatment they received or are receiving. The Registry will be conducted under conditions of routine clinical practice, without registry-mandatory assessments according to the treating physician and will include all eligible patients who agree to participate.

Within the Registry, a pool of patients with alpha-mannosidosis undergoing Lamzede therapy will be suitable to allow a further data collection revolved to the long-term safety and effectiveness of Lamzede therapy (see Section 9.7.4 for the study endpoints). In this group of patients, Lamzede has to be administered in accordance with the current Lamzede SmPC and in line with usual clinical practice. Patients with alpha-mannosidosis receiving and not receiving Lamzede will be also enrolled. It is expected that the pool of patients not receiving Lamzede will be limited in number and characterized by distinct clinical features and/ or a short follow-up duration. This does not permit the definition of a control group and a direct, formal determined *a-priori* between-group comparison, allowing for a descriptive, explorative between-groups comparison only.

Clinical Protocol Number: CLI-LMZYMAA1-12

Clinical Protocol Version Number: 8.0

If applicable in accordance with routine clinical practice, the following schedule of visits is recommended:

- **Registry Inclusion Visit**, at the time of enrolment into the Registry approximately 7 days prior to the Registry Baseline visit. In order to check eligibility criteria and when the informed consent form could also be signed in case to patient willingness to participate to the study;
- **Registry Baseline Visit**, corresponding for all patients included, to the time in which the observational period will start (Time 0) and when the site can also evaluate to possibly start or continue the treatment with Lamzede according to clinical practice;
- Six-month and Yearly follow-up visits for all patients included in the registry;
- Unscheduled follow-up visits, such as but not limited to, three months after Lamzede treatment start, or whenever deemed appropriate, according to treating physician's judgement for patients that start Lamzede treatment within one year prior to Registry inclusion. During the following years, routine clinical visits are recommended to take place at least annually, for all patients.

As patients can start Lamzede treatment at any time during the course of their participation to the Registry, if applicable in accordance with routine clinical practice, a baseline visit is recommended to be repeated before Lamzede administration starts and unscheduled visits are recommended as detailed in the setting of patients that start Lamzede treatment within one year prior to Registry inclusion. On the other hand, the patients can also terminate the Lamzede treatment at any time during the course of their participation to the Registry, completing in any case the 15-year follow-up period.

A schematic diagram is reported in Figure 4.

* If applicable in accordance with routine clinical practice, unscheduled follow-up visits can be performed at, but not limited to, three months after Lamzede treatment start, or whenever deemed appropriate according to treating physician's judgement for patients that start Lamzede treatment within one year prior to Registry inclusion.

** Patients can start Lamzede treatment at any time during the course of their participation to the Registry, if applicable in accordance with routine clinical practice, a baseline visit is recommended to be repeated before Lamzede administration starts and unscheduled visits are recommended as reported in the schema above

Clinical Protocol Number: CLI-LMZYMAA1-12	
Clinical Protocol Version Number: 8.0	Date: 01 February 2019

The investigator will report data for study endpoint assessments during the data reporting periods outline in Table 1.

9.2 Setting

9.2.1 Subject Recruitment

The eligible patient population for this Registry includes any patient in the EU suffering from alpha-mannosidosis who is willing to participate, and who meets the inclusion criteria (see below) for this Registry. The recruitment period will be indefinite.

About 30 patients are foreseen as coming from previous Lamzede clinical trials. Each patient will be followed-up for 15 years.

Based on the current unmet medical need, patients can start Lamzede treatment independently from the Registry set up.

9.2.2 Inclusion Criteria

To be eligible for enrolment in the Registry, patients must fulfil all the following inclusion criteria:

- 1. Evidence of a personally signed and dated informed consent form indicating that the patient (or parents or a legally acceptable representative according to local regulation) has been informed of all pertinent aspects of the Registry and confirms the willingness to participate to the present observational study and permits the investigator to enter assessment data recorded prior to Registry entry if available in the patient's medical records.
- 2. Diagnosis of alpha-mannosidosis (based on historical or current diagnosis).

9.2.3 Exclusion Criteria

There are no exclusion criteria for the Registry.

Moreover, patients participating in other clinical trials of any placebo, drug or biological substance conducted under the provisions of a protocol will not be prevented to participate to the Registry at the discretion of the Investigator.

9.2.4 Patient Withdrawal

Patients may be discontinued from the study at any time for any of the following reasons:

- The patient is lost to follow-up.
- The patient withdraws consent and is unwilling to continue the registry participation.
- The sponsor or the regulatory authorities or the Ethics Committees (ECs), for any reason, terminates the entire study, or terminates the study for this study site or this particular patient.

It is understood by all concerned that an excessive rate of withdrawals can render the study not interpretable; therefore, unnecessary withdrawals of patients should be avoided.

However, should a patient discontinue the study, all efforts will be made to complete and report the observations as thoroughly as possible.

In case a patient is transferred to another continuing care site, the new treating site will be formally involved in the Registry study following a request of authorization submitted to the relevant Ethics

Clinical Protocol Number: CLI-LMZYMAA1-12

Clinical Protocol Version Number: 8.0	Date: 01 February 2019

Committee and Regulatory Authority to complete the 15-year observational period following the patient and collecting all information as per study protocol.

In case of withdrawal, the investigator must fill in the "Study Termination" page in the electronic Case Report Form (eCRF), reporting the main reason for withdrawal.

In order to collect as complete as possible information in the clinical study database, all ADRs and SAEs ongoing at the time the patient's study participation ends should be evaluated up to 14 days after last Lamzede intake. After this period, all unresolved ADRs and SAEs will be reported as "ongoing" in the eCRF.

If a patient is withdrawn from the registry, after having started or continued the treatment with Lamzede, the investigator should report to the sponsor any post-discontinuation new serious adverse event causally related to Lamzede he/she may have knowledge of.

If a patient is withdrawn/drops-out of the study the patient study number should not be reassigned to another patient.

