9.7 Data Analysis

The following describes the statistical analysis as it is foreseen at the time of planning the trial. Detailed methodology for the summary and statistical analyses of data collected in this study will be documented in a Statistical Analysis Plan (SAP).

9.7.1 Populations for Analysis

The following analysis sets will be defined:

- The Lamzede Safety analysis set (L-SAF) will contain all enrolled patients fulfilling inclusion criteria who have, at some time, received Lamzede treatment. This will include all patients entering the study currently taking Lamzede and all patients not taking Lamzede on entry to the study, but who begin doing so during the study. The latter group (those not taking Lamzede on entry to the study, but who begin doing so during the study) will only be classed as in the L-SAF from the time that they begin taking Lamzede. As is common practice, patients who have taken any amount of Lamzede, even if only one dose, will be included in the safety analyses. With regards to L-SAF definition, a minimum individual follow up of 1 month after last dose taken will be proposed. A consequence of this approach, where patients can be in the L-SAF for very varying amounts of time is that adverse event (and adverse reaction) rates will be presented based on person-years at risk, and not simply based on the total number of patients who are ever in the L-SAF.
- The Lamzede Effectiveness analysis set (L-FAS) will contain patients included in the Lamzede Safety analysis set at the times when they have been taking Lamzede, and for 12 months thereafter excluding patients without any valid measurement and those with major protocol deviations affecting the effectiveness evaluations. The consequence of this is that

Clinical Protocol Number: CLI-LMZYMAA1-12	
Clinical Protocol Version Number: 8.0	Date: 01 February 2019

"baseline" will be clearly defined for each patient – namely the time they started to take Lamzede, not necessarily the time they enter the study. So a patient can be excluded from the L-FAS for some of their time in the study, and then join the L-FAS. In such cases, their "baseline" would be the time when they started.

- The No-Lamzede Safety analysis set (NL-SAF) will include patients only for the time when they are not (and have not within 1 month) been taking Lamzede.

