11.7 Outcome

Each AE must be rated by choosing among:

- Recovered/resolved.
- Recovering/resolving.
- Not recovered/not resolved.
- Recovered with sequelae/resolved with sequelae.
- Fatal.
- Unknown.

Clinical Protocol Number: CLI-LMZYMAA1-12

Clinical Protocol Version Number: 8.0

11.8 Recording of Adverse Events

All AEs occurring during the course of the study must be documented in the AE page of the eCRF. Moreover, if the AE is related to the study drug, the AE form must be also completed.

It is responsibility of the investigator to collect all AEs (both serious and non-serious) derived by spontaneous, unsolicited reports of patients, by observation and by routine open questionings.

The recording period for AEs is the period starting from the Informed Consent signature until the patient's study participation ends.

If a clinically significant abnormal laboratory finding or other abnormal assessment meets the definition of an AE, then the AE eCRF page must be completed, as appropriate. A diagnosis, if known, or clinical signs and symptoms if diagnosis is unknown, rather than the clinically significant abnormal laboratory finding, should be reported on AE eCRF page. If no diagnosis is known and clinical signs and symptoms are not present, then the abnormal finding should be recorded.

In order to collect as complete as possible information in the clinical study database, all ADRs and SAEs ongoing at the time the patient's study participation ends should be evaluated up to 14 days after last study drug intake. After this period, all unresolved ADRs and SAEs will be reported as "ongoing" in the eCRF.

For pharmacovigilance purposes, all SAEs should be followed-up in order to elucidate as completely and practically as possible their nature and/or causality until resolution of all queries, clinical recovery is complete, laboratory results have returned to normal, stable condition is reached or the patient is lost to follow-up. Follow-up may therefore continue until after the patient has left the study up to 30 days after his/her discontinuation from the study for unrelated SAEs, and without timelines for related SAEs.

11.9 Reporting Serious Adverse Events to Chiesi

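### The rule for following up ADRs and SAEs open at study exit is counted from the last Lamzede intake, so it gives no usable window to patients who are off treatment or never treated

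*Protocol*

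**What the plan says.** Section 9.2.4 (Patient Withdrawal) states that "all ADRs and SAEs ongoing at the time the patient's study participation ends should be evaluated up to 14 days after last Lamzede intake". The next sentence begins "After this period, all unresolved ADRs and SAEs will be reported as" and gives the entry as ongoing in the eCRF. Section 11.8 (Recording of Adverse Events) repeats the rule: such events "should be evaluated up to 14 days after last study drug intake". It gives the purpose as "In order to collect as complete as possible information in the clinical study database".

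Section 11.8 then sets a second follow-up with a different purpose: "For pharmacovigilance purposes, all SAEs should be followed-up". This may continue "up to 30 days after his/her discontinuation from the study for unrelated SAEs, and without timelines for related SAEs".

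Four other parts of the protocol bear on the point:

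- **Who is enrolled and for how long.** Section 9.1 enrols both treated and untreated patients. Patients may start or stop Lamzede at any time and are followed for 15 years in either case.
- **AE recording.** Under 11.8 it runs from consent to the end of participation, whatever the treatment status.
- **Safety summaries.** Section 9.7.5 plans proportions of patients with events, event counts and person-time rates. AEs leading to death are a named category, to be included whenever they become known.
- **Outcome codes.** Section 11.7 lists six permitted outcomes. Fatal is one of them; ongoing is not.

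**The concern.** A 14-day tail after the last dose makes sense in a trial where treatment and participation end together. Here they do not. A patient may have stopped Lamzede long before leaving, may never have received it, or may leave while treatment continues. The rule starts from one date and is measured from another, so for some patients there is nothing to evaluate: the open event goes straight to ongoing.

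What is at stake is the outcome of events still open at exit. Section 11.1 treats death as an outcome of an AE and not as an AE in itself. An SAE that is open at exit and later proves fatal can therefore be counted under AEs leading to death only if its outcome is updated. The database rule stops that update early, or never allows it. For SAEs the later outcome is meant to be collected anyway under the pharmacovigilance follow-up. For non-serious ADRs the protocol states no longer follow-up.

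**Working it through.** The plan gives no calculated figure on this point, so the check is date arithmetic on its stated windows.

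**Inputs.** Database window: 14 days from last intake (9.2.4, 11.8). Pharmacovigilance window for unrelated SAEs: 30 days from study discontinuation (11.8). Dosing: weekly (Table 1 footnote 6, 9.3.2). Let g be the number of days from last Lamzede intake to study exit.

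**Formulas.** Days of database evaluation left at exit = 14 − g. Counted from the last dose, the SAE window for unrelated events closes on day g + 30, so it closes (g + 30) − 14 = g + 16 days after the database window.

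| g (days) | Evaluation left at exit, 14 − g | Gap between the two limits, g + 16 |
|---|---|---|
| 0 | 14 | 16 |
| 7 | 7 | 23 |
| 14 | 0 | 30 |
| 30 | −16 | 46 |
| 365 | −351 | 381 |
| 730 | −716 | 746 |

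For related SAEs the second window has no limit, so the gap is open-ended.

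**By treatment status at exit.**

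1. *On weekly Lamzede at exit.* If the last intake is read as the last dose before exit and no infusion was missed, g lies between 0 and 7, leaving 14 to 7 days. The text does not say this is what is meant. If treatment continues after exit, the last intake has not yet happened and the limit is undefined.
2. *Off Lamzede for more than 14 days.* The result is negative: the window closed before the patient left.
3. *Never treated.* g does not exist, so the window has no start.

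**Consequence for the analysis sets.** Section 9.7.1 counts time in NL-SAF only when the patient has not taken Lamzede within 1 month. Taking a month as 30 days, anyone who exits during NL-SAF time has g of at least 30 or no g at all, and so has no evaluation after exit. A patient exiting on treatment has about 7 to 14 days under the favourable reading. Ascertainment of outcomes at exit therefore differs by treatment status.

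**Which planned outputs can change.** Whether an event occurred, how many events there were and the person-time at risk do not depend on how an open event ends. The category of AEs leading to death does.

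**The case against.** The strongest defence is that the two follow-up rules in 11.8 have separate stated purposes, one for the study database and one for pharmacovigilance, so SAEs are not lost to follow-up. Deaths are also covered elsewhere: 9.7.5 includes fatal AEs whenever they become known, and 11.12 requires a death narrative to be sent to the safety contact. Reconciliation of SAEs between databases is often set out in data-management or safety plans that are not shown here. Loss to follow-up and withdrawn consent are among the exit routes in 9.2.4, and a better-placed window may recover little from those patients.

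Much of this stands, and it rules out several stronger readings that a reader might infer:

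- *That the rule fails for most patients.* No distribution of treatment status at exit is given, 9.1 expects few untreated patients, and for those on weekly treatment a sensible reading leaves 7 to 14 days.
- *That the 30-day or unlimited SAE follow-up contradicts the 14 days.* It serves a different stated purpose. The weakness is that the two records can differ, with no stated step to align them.
- *That the L-SAF period contradicts the 14 days.* Section 9.7.1 says that "a minimum individual follow up of 1 month after last dose taken will be proposed". That is follow-up for an analysis set, which is a different quantity from following an existing event to its outcome.
- *That safety results in general are biased or deaths are understated.* Counts and rates do not move, and no understated death count is shown.

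The defence does not repair the anchor. No reading of the last intake gives a window to a never-treated patient, or an open one to a patient who stopped more than 14 days before leaving. The wording on fatal AEs in 9.7.5 also pulls against the instruction to enter open events as ongoing, and the protocol does not say which prevails.

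**Conclusion.** The concern holds in a limited form. The rule in 9.2.4 and 11.8 does not work for patients off Lamzede for more than 14 days at exit or never treated, and it is ambiguous for those who continue treatment after exit. In off-treatment patients, ADRs and SAEs open at exit get no evaluation in the study database and are recorded as ongoing, while 11.8 requires longer follow-up of the SAEs elsewhere.

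The effect is confined to events open at exit. Occurrence, counts and person-time rates are unaffected; the exposed output is AEs leading to death. How many patients are involved cannot be stated, because the protocol gives no figures for treatment status or open events at exit. With a planning figure of at least 70 treated patients (9.5), a single death recorded as ongoing would be noticeable in that category, but nothing in the protocol shows that this will happen.

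The 7 to 14 days for on-treatment patients assumes uninterrupted weekly dosing and that the last dose before exit is meant. The results for off-treatment and never-treated patients follow from the text without assumptions. The point merits correction because sites act on this wording when they close a patient's record, and an outcome not collected then may not be recoverable.

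**What to change.** 1. In 9.2.4 and 11.8, count the eCRF rule from the end of study participation for all patients, whatever their treatment status. The length of the window, including for non-serious ADRs, is for the sponsor to set, but it should not be tied again to the last dose.
2. For SAEs open at exit, update the eCRF outcome from the follow-up that 11.8 already requires, at reconciliation before each data cut and up to database lock (9.6). The lock puts an end to what would otherwise be an unlimited update for related SAEs.
3. Replace ongoing with one of the categories in 11.7.
4. Reconcile 9.2.4, 9.7.5 and 11.8, so that it is clear how a fatal outcome learned after exit enters the summary of AEs leading to death.

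The cost is wording in these sections and an outcome update at reconciliation. No new SAE follow-up is asked for. The small downside is a later final entry for patients who leave with an open event.
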